CD = cluster of differentiation; ELISA = enzyme-linked immunosorbent assay; ELISpot = enzyme-linked immunosopt (assay); ICS = intracellular cytokine staining; IFN γ = interferon gamma; IL = interleukin; PBMC = peripheral blood mononuclear cell; RNA = ribonucleic acid; SARS-CoV-2 = severe acute respiratory syndrome coronavirus-2; Th = T helper; TNF α = tumor necrosis factor alpha; VNA = virus neutralization assay.

Handling of Missing and/or Unguantifiable Immune Response Data 5.7.1.2.

Missing immune response data will not be imputed.

Values below the lower limit of quantification (LLOQ) or limit of detection (LOD) will be handled as follows:

- Calculation of geomean and median:
 - values<LLOQ are imputed with LLOQ/2.
- Calculation of fold changes from baseline:
 - values <LLOQ are imputed with LLOQ.

Values above the upper limit of quantification (ULOQ) will be handled as follows:

- Calculation of geomean and median:
 - Values>ULOQ are imputed with ULOQ.
- Calculation of fold changes from baseline:
 - Values >ULOQ are imputed with ULOQ.

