5.7.1.5. Immunogenicity Against the Insert

5.7.1.5.1. Humoral Assays

For **VNA** (both wild-type virus and pseudovirion expressing S protein, as available), the following statistics will be calculated: N, geometric mean, and corresponding 95% CI of the actual values, fold change from baseline and fold change from pre-booster (for time points after booster vaccination). In some cases, fold change from other timepoints may also be calculated. Geometric mean ratio and CI will be calculated at each post baseline visit.

For the calculation of the geometric mean and its corresponding 95% CI, the arithmetic mean, and its corresponding 95% CI are calculated on the log₁₀ transformed values. These values are back transformed to provide the geometric mean and its corresponding 95% CI.

For wild-type and pseudovirion VNA separately:

- A sample will be considered positive if the value is strictly greater than the LLOQ (>LLOQ).
- Responder definition (in adults): A post-baseline sample will be considered a responder if at least one of the following conditions is satisfied:
 - $\circ~$ The baseline sample value is less than or equal to the LLOQ (\leq LLOQ) and the post-baseline sample value is strictly greater than the LLOQ (>LLOQ)
 - The baseline sample value is strictly greater than the LLOQ (>LLOQ) and the post-baseline value represents an at least 4-fold (\geq 4-fold) increase from the baseline sample value.

Actual values are tabulated and shown as dot plots with dots for participant values, and the corresponding geometric mean and 95% CI per time point for each assay. In addition, GMT plots over time without individual participant dots will also be generated. Participant profiles of the actual values over time will be graphically presented.

For infants born to vaccinated mothers, tables and graphs will be made per the vaccine regimen of the mother. In addition, in the neonate profiles of the actual values over time, the mother's value at birth will be added to visualize transfer of binding or neutralizing antibodies to the newborn.

In the graphs, original values will be displayed on the log_{10} scale.

Further details and/or updated rules will be provided in the DPS.

For the exploratory **variant SARS-CoV-2 neutralization assays** (different from the VNA used for the secondary endpoint), the same as above applies.

For **S-ELISA** and **MSD 4-PLEX**, the same as above applies.

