The ratio of binding antibodies (S-ELISA measured by S-ELISA or MSD 4-PLEX assay) to wild type VNA, the ratio of binding antibodies (S-ELISA measured by S-ELISA or MSD 4-PLEX assay) to pseudovirion expressing S protein VNA, and the ratio of binding antibodies (S-ELISA measured by S-ELISA or MSD 4-PLEX assay) to the VNAs measured by alternative assays will be calculated for each time point. Values <LLOQ will be imputed with LLOQ for the calculation of the ratios. In addition, the ratio of the fold change from baseline in binding antibodies (S-ELISA measured by S-ELISA or MSD 4-PLEX assay) to the fold change from baseline in VNA, will be calculated for each post-baseline time point. Values <LLOQ will be imputed with LLOQ for the calculated for each post-baseline time point. Values <LLOQ will be imputed with LLOQ for the calculation of the fold change ratios. The following statistics will be calculated and tabulated: N, geometric mean and corresponding 95% CI of the ratio. Graphical displays will also be prepared, showing – for each time point – the geometric mean of the ratio and its 95% CI, together with the individual data points (dot plot).

If a similar assay is performed at different analyzing labs, then separate statistical analyses may be performed.

Scatterplots between humoral assay results (as available) will be provided for selected time points. These may be included but are not limited to:

- Binding antibodies (S-ELISA measured by S-ELISA or MSD 4-PLEX assay) versus VNA (wild type VNA, psVNA or variant VNA)
- wtVNA versus psVNA
- wtVNA versus variant VNA
- psVNA versus variant VNA
- Ad26 VNA versus S-ELISA
- Ad26 versus wtVNA
- Ad26 versus psVNA and/or variant VNA

If a similar assay is performed at different analyzing labs, then the statistical analyses may distinguish between these and provide separate scatterplots for each analyzing lab versus the other assay of interest. These scatterplots will display the values as analyzed for the geometric mean calculations, with values <LLOQ imputed with LLOQ (if an LLOQ is defined) and values >ULOQ imputed with ULOQ (if an ULOQ is defined). The LLOQ and ULOQ cut-off values per assay will be visualized in the scatterplots. Spearman correlation coefficients will also be provided (one per scatterplot).

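### The binding-to-VNA ratio sets values below LLOQ to LLOQ with no evaluability condition, so doubly censored pairs yield an assay constant and VNA-censored pairs a lower bound averaged as if measured

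*SAP*

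**What the plan says.** Section 5.7.1.5.1 defines ratios of binding antibody (S-ELISA or MSD 4-plex) to wild-type, pseudovirion and other VNAs. The list closes with "to the VNAs measured by alternative assays will be calculated for each time point", so baseline is included. The handling rule is "Values <LLOQ will be imputed with LLOQ for the calculation of the ratios", and the reported statistics are "N, geometric mean and corresponding 95% CI of the ratio", with a plot of individual points. The section's general method applies: mean and interval on the log10 scale, and then "These values are back transformed to provide the geometric mean and its corresponding 95% CI".

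A second quantity, the ratio of the fold change in binding to the fold change in VNA, uses the same LLOQ rule but only after baseline.

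The general rules in Section 5.7.1.2 are "values<LLOQ are imputed with LLOQ/2" for geometric means and medians, and "values<LLOQ are imputed with LLOQ" for fold changes.

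Nothing in the section excludes, counts or flags pairs in which one or both values were below LLOQ. Section 5.7.1.5.2 treats the Th1/Th2 ratio differently. That ratio is post-baseline only and needs at least one response that is positive and at least twice LLOQ. It is numeric only when both responses qualify, and is otherwise reported as above or below 1.

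**The concern.** A ratio of two assay results carries information about antibody only where the results were measured. Once limits are substituted, the tabulated mean partly reports the assay limits and the share of samples below them. Two groups or visits with the same true ratio can then look different because more VNA values are censored in one of them.

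Section 5.7.5 presents key S-ELISA, MSD and VNA results by baseline serostatus and previous vaccination group. A seronegative, vaccine-naïve baseline cell could therefore stand beside cells from previously vaccinated women whose ratios are real measurements, with nothing in the table to tell them apart.

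**Working it through.** The SAP gives no expected ratio, SD or humoral LLOQ, so there is no planned figure to reproduce.

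**Inputs.** From the SAP: the LLOQ rule, the log10 mean and interval, and group targets of at least 25 (Group 4) and at least 40 (Groups 1 to 3). Assumed: log10 titers bivariate normal, SD 0.5 in each assay, correlation 0.3 to 0.9, and the mean titers. Each assay is expressed in units of its own LLOQ, so the limit is 0 on the log10 scale.

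**Algebra, no assumptions needed.**
- Both below LLOQ: ratio = LLOQ(binding) / LLOQ(VNA), identical for every such woman, SD 0. Substituting LLOQ/2 in both assays would give the same constant.
- Only VNA below LLOQ: ratio = measured binding / LLOQ(VNA). The true denominator is smaller, so this is a lower bound. It still varies between women.
- Fold-change ratio: exactly 1 if both assays are below LLOQ both at baseline and at the later visit.

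**Where double censoring is likely.** Table 7 calls a Group 4 woman seronegative if N serology and S-ELISA are both negative. Section 5.7.1.5.1 makes a value above LLOQ the positivity criterion for VNA and applies the same to S-ELISA. On that cut-off every S-ELISA numerator in this cell equals LLOQ at baseline. VNA below LLOQ there is an assumption.

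**Size of the bias.** With X normal (mean μ, SD σ) and values below 0 set to 0, the mean is μΦ(μ/σ) + σφ(μ/σ). The mean log10 ratio under the SAP rule is this quantity for binding minus that for VNA, so it does not depend on the correlation. Take a true ratio of 10^0.5 = 3.16, that is, μ(binding) = μ(VNA) + 0.5:

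| VNA < LLOQ | μ(VNA) | Binding < LLOQ | Binding mean − VNA mean | Tabulated ratio |
|---|---|---|---|---|
| 20% | 0.421 | 3% | 0.927 − 0.477 = 0.451 | 2.82 |
| 50% | 0.000 | 16% | 0.542 − 0.199 = 0.342 | 2.20 |
| 80% | −0.421 | 44% | 0.242 − 0.056 = 0.186 | 1.53 |

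Differences are taken before rounding. Some binding values are censored too, so the last row mixes single and double censoring.

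**Intervals (simulation, n = 25; n = 40 is alike).** Half-widths are on the log10 scale, relative to the same data uncensored.
- Both assays low (binding 84–98%, VNA 98–100% below LLOQ): true ratio 3.16 or 2.00, tabulated 1.09 or 1.01; half-width 0.04 to 0.47 times; coverage 0%.
- Binding measurable, VNA 84% below LLOQ: true ratio 31.6 or 100, tabulated about 9.2 or 28.7, roughly 3.5-fold too low. Half-width 0.82–0.83 times at correlation 0.3, 1.02–1.05 at 0.6 and 1.93–1.97 at 0.9; coverage about 0%.
- VNA 8% below LLOQ: true ratio 6.31, tabulated 6.01–6.06; half-width 0.97–1.03 times; coverage 93–95%.

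**Possible remedies (true ratio 3.16).**

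| VNA < LLOQ | Correlation | SAP rule | Drop doubly censored pairs | Only pairs quantifiable in both |
|---|---|---|---|---|
| 20% | 0.3 | 2.83 | 2.87 | 2.52 |
| 50% | 0.3 | 2.20 | 2.42 | 2.02 |
| 50% | 0.8 | 2.20 | 2.54 | 2.68 |
| 80% | 0.8 | 1.53 | 2.12 | 2.39 |

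Dropping doubly censored pairs is closer to the truth than the SAP rule in every row. Keeping only quantifiable pairs selects on the denominator and is worse than the SAP rule at correlation 0.3 in the first two rows.

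**The case against.** The strongest reply is that little depends on this ratio. It is not a listed endpoint; the exploratory endpoint is the ELISA–VNA correlation, reported with Spearman coefficients and scatterplots that mark the quantification limits. No immunogenicity hypothesis is tested, the individual ratios are plotted so that a stack of identical values would be visible, and the Data Presentation Specifications may add rules. All of this stands and limits the weight of the point. It does not repair a tabulated mean and interval that partly describe assay limits, and the SAP states the substitution rule outright.

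A reader might infer more: that in any woman with little neutralizing antibody the ratio is a quotient of two limits with a falsely tight interval. The documents do not support that. Binding must also be below LLOQ, and previously vaccinated women, or naïve women after vaccination, may have measurable binding antibody with low VNA. Their ratio is a varying lower bound, and its interval can be up to about twice as wide as the uncensored one. The general fault in that case is the centre of the estimate.

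It is also fair to say that every magnitude rests on assumed SDs, correlations and means, because the SAP gives neither humoral LLOQs nor expected shares below them.

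**Conclusion.** The point holds as a minor one. That doubly censored pairs return an assay constant follows from the rule alone. That this fills the seronegative Group 4 baseline cell rests on VNA being below LLOQ there, and for the numerator on S-ELISA being the binding assay. With only VNA censored, the geometric mean is biased low by an amount that follows the share censored: negligible at 8%, and about two-fold at 80% for a true ratio of 3.16 (3.16 / 1.53 = 2.1), where double censoring also contributes. No general statement that the intervals are too narrow is justified. The fold-change ratio needs no change of rule: it is post-baseline only and follows the SAP's general LLOQ rule for fold changes. The primary S-ELISA endpoint is unaffected.

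**What to change.** In Section 5.7.1.5.1, for the binding-to-VNA ratio:
- Exclude pairs in which both values are below LLOQ.
- Print the numbers of singly and doubly censored pairs beside N.
- Show no geometric mean or interval for a time point and group where most pairs are not quantifiable in both assays, in particular baseline in seronegative Group 4.
- Where a summary is wanted despite single censoring, estimate it with a bivariate censored-normal likelihood on the log10 scale. Do not use a mean over quantifiable pairs only, which can be more biased at low correlation.

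Leave the fold-change ratio on the general LLOQ rule and add counts of participants with censored values. Requiring quantifiable values throughout would remove women with a baseline below LLOQ from that analysis at every later visit, however strong their response.

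The cost is a few lines of SAP text and minor programming, with fewer contributing pairs and some blank cells at low-titer time points. Dropping doubly censored pairs does not remove the bias from single censoring (2.12 against a true 3.16 in the last row of the remedies table), which is why the counts must be shown.

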5.7.1.5.2. Cellular Assays

For **ELISpot**, if available, at least the following statistics will be calculated: N, median, first and third quartile, minimum and maximum of the actual values. Additional statistics may be calculated and will be detailed in the DPS. The ELISpot in this study is planned to be a dual ELISpot, measuring IFN-gamma and IL-4. In that case, the statistics will be analyzed for each cytokine separately.

For each cytokine, if available, the following is defined:

• Sample positivity:

For IFN-g: a sample will be considered positive if the value is strictly greater than the LOD (>LOD)

For IL-4: a sample will be considered positive if the value is strictly greater than the LOD (>LOD)

• Responder:

A post-baseline sample will be considered a responder if at least one of the following condition is satisfied:

CONFIDENTIAL – FOIA Exemptions Apply in U.S.

For IFN-g:

- The baseline sample value is less than or equal to the LOD (<LOD) and the post-baseline sample value is strictly greater than the LOD (>LOD).
- The baseline sample value is strictly greater than the LOD (>LOD) and the post-baseline sample value represents an at least 3-fold (≥3-fold) increase from the baseline sample value.

For IL-4:

- The baseline sample value is less than or equal to the LOD (≤LOD) and the post-baseline sample value is strictly greater than the LOD (>LOD).
- The baseline sample value is less than or equal to the LLOQ (≤LLOQ) and the postbaseline sample value is strictly greater than the LLOQ (>LLOQ).
- The baseline sample value is strictly greater than the LLOQ (>LLOQ) and the postbaseline sample value represents an at least 2-fold (≥2-fold) increase from the baseline sample value.

The SDTM database will contain the LOD and LLOQ values.

In keeping with the general derivation rules, values <LLOQ are imputed with LLOQ/2 for the calculation of the median and with LLOQ for the calculation of the fold changes from baseline.

ELISpot values available in the database will already be background subtracted. No further background subtraction should be carried out.

Tables with the descriptive statistics will be provided.

Participant profiles of the actual values over time will be graphically presented. For the graphs, original values will be displayed on the log_{10} scale.

For ELISpot, the reported values are spot forming cells per million peripheral blood mononuclear cells (PBMC).

For ELISpot, IFN-g responses are considered Th1 and IL-4 responses are considered Th2. Due to this 1-to-1 correspondence, no separate Th1/Th2 analyses will be conducted for ELISpot.

Further details and/or updated rules will be provided in the DPS.

For **ICS**, if available, following statistics will be calculated: N, median, first and third quartile, minimum and maximum of the actual values, number, and percentage of participants with a positive sample (if available). Additional statistics may be calculated and will be detailed in the DPS.

It is planned to analyze the following cell populations. The DPS may provide an updated version of this list, e.g. for subsequent analyses.

For CD4+:

- IFN-g or IL2
- IFN-g or IL2 NOT TH2
- IL4 and CD40L
- IL4 or IL5 or IL13 and CD40L

For CD8+:

- IFN-g or IL2

The data received from the analyzing lab(s) will contain background subtracted values ("Immediately reportable values"; i.e. background subtracted^a percentage of cells expressing the cytokine or cytokine combination). Negative background subtracted values will be imputed with zero prior to further processing.

The data will contain a positivity call for each cell population. Sample positivity should therefore not be further derived at the statistical analysis stage.

Tables will be provided that show the descriptive statistics mentioned above, structured as follows: CD4+/CD8+, peptide pool (as available in the database, e.g. SARS-Cov2-S, SARS-Cov2-S, SARS-Cov2-S1, SARS-Cov2-S2), cytokine (combination), and time point.

Participant profiles of the actual values over time will be graphically presented. For the graphs, original values will be displayed on the log_{10} scale, with values <0.022% imputed with 0.011% (only for visual representation; calculations will be based on the actual values). The graphs that show individual participant data will visually differentiate between positive/negative samples (e.g. different symbols and/or different colors)

The reported values are percentage of cells expressing the cytokine(s).

Assessment of Th1/Th2 response ratio

Based on the combined SARS-Cov2-S peptide pool, and using post baseline time points only, a Th1/Th2 response ratio will be calculated for samples that satisfy at least one of the following two conditions:

- a Th1 response ("IFN-g or IL2 NOT TH2") that is both positive and $\geq 2 \times LLOQ$,

or

- a Th2 response ("IL4 or IL5 or IL13 and CD40L") that is both positive and $\geq 2 \times LLOQ$

^a Also known as "mock subtracted"

For the purposes of the Th1/Th2 ratio analysis, the LLOQ is 0.022% for both cell populations (Th1 and Th2).

If both cell populations (Th1 and Th2) are positive and $\geq 2 \times LLOQ$, then the ratio of Th1/Th2 will be calculated as a numerical result.

If only one cell population (either Th1 or Th2) is positive and $\ge 2 \text{ x LLOQ}$, then the following rules will be used to determine a qualitative assessment of the Th1/Th2 ratio:

- If one cell population is positive and the other is negative, then the positive cell population is greater than the negative cell population: if the Th1 response is positive and the Th2 response is negative, then the Th1/Th2 ratio will be set to ">1". If the Th1 response is negative and the Th2 response is positive, then the Th1/Th2 ratio will be set to "<1".
- If both cell populations are positive, then the cell population that is $\ge 2 \times LLOQ$ is greater than the cell population that is $< 2 \times LLOQ$: if the Th1 response is $\ge 2 \times LLOQ$ and the Th2 response is $< 2 \times LLOQ$, then the Th1/Th2 ratio will be set to ">1". If the Th1 response is $< 2 \times LLOQ$ and the Th2 response is $\ge 2 \times LLOQ$, then the Th1/Th2 ratio will be set to "<1".

For each post baseline time point, the number of participants with an evaluable Th1/Th2 response ratio will be tabulated, together with the number and percentage of participants with a Th1/Th2 ratio ≥ 1 and the number and percentage of participants with a Th1/Th2 ratio < 1. Graphical display(s) of these data may also be produced.

Further details and/or updated rules will be provided in the DPS.

5.7.1.6. Immunogenicity Against the Vector

If available, for immunogenicity against the Ad26 vector backbone (Adenovirus neutralization by neutralization assay), the following statistics will be calculated: geometric mean and corresponding 95% CI of the actual values, and number and percentage of participants with a positive sample.

Immunogenicity against the vector may also be assessed in cord blood and in newborns to assess the transfer of Ad26 neutralizing antibodies to newborns.

Correlation plots with the Ad26 assays versus the assays against the inserts will be provided for the most important time points.

5.7.1.7. Biomarkers

For all adult participants, biomarker analysis (PAXgene®, RNA-seq) will be performed to explore potentially informative biomarkers related to vaccine immunogenicity and SARS-CoV-2 infection (including relations with COVID-19 severity).

For adult participants with a positive test result for SARS-CoV-2 infection, biomarker analysis (PAXgene®, RNA-seq) will be performed for evaluation of COVID-19 cases and to explore potentially informative biomarkers, correlating with SARS-CoV-2 infection and COVID-19 severity, at Day 3 to 5 and at Day 29 (\pm 7 days) after onset of symptoms.

5.7.2. Occurrence of Symptomatic Molecularly Confirmed and Asymptomatic COVID19

An immunologic test for SARS-CoV-2 seroconversion (non-S ELISA and/or SARS-CoV-2 immunoglobulin assay) based on SARS-CoV-2 N-protein, will be performed in adult participants to identify cases of asymptomatic infection. The presence of SARS-CoV-2 infection will be assessed at the study site by molecular testing RT-PCR or molecular test result from any available respiratory tract sample. Asymptomatic infections also include those detected by confirmed molecular tests (either in this study or outside study), in the absence of the relevant symptoms.

Procedures to be performed in the event a participant (adult or infant/neonate) experiences signs or symptoms suggesting possible COVID-19 are detailed in CTP Sections 1.3 and 8.1.2. A sign or symptom is considered as absent or present for a COVID-19 episode if observed in the eCOA or eCRF for the COVID-19 episode, and absent if not.

COVID-19 episodes will not be adjudicated. All data presented corresponding to the COVID-19 episode will be based on the SIC (or PedSIC) as detailed in Section 5.7.3.

The following analyses will use the FAS-A set and will be conducted at the time of the final analysis:

The number and percentage of participants with at least one molecularly confirmed symptomatic or asymptomatic SARS-CoV-2 infection will be tabulated by post vaccination visit and for the entire study period. Similar table will be produced for infants.

The number and percentage of participants who are positive by N serology at different time points will be tabulated.

5.7.3. COVID-19 signs and symptoms

5.7.3.1. Symptoms of Infection with Coronavirus-19 (SIC)

The SIC is a disease-specific patient-reported outcome (PRO) instrument that is completed by the participant. The SIC has a total of 30 items assessing signs and symptoms of COVID-19. The first 25 items, the participant indicates "yes" or "no" if they have a symptom and if "yes" report a severity from 0 (none) to 10 (worst possible). The second part has the participant enter their temperature, and the third part has the participant record "yes" or "no" (absence or presence of additional signs and symptoms), where severity cannot be assessed). The analyses are conducted in two ways, by part 1, part 2 and part 3, scored separately, and also grouped into related categories for composite scoring.

